7 STATISTICAL METHODS

7.1 General Principles

All data processing, summarization and analyses will be performed using the Hosted SAS Environment Version 9.3 (or later) of the SAS[®] statistical software package.

Unless specified otherwise, data will be displayed using the following treatment group labels, in the order presented:

- Control,
 - those who are on Idarubicin + Cytarabine therapy only
- Low CX-01,
 - those who are on Idarubicin + Cytarabine + plus lower dose CX-01
- High CX-01,
 - those who are on Idarubicin + Cytarabine + plus higher dose CX-01
- Overall

All data collected will be presented in listings by treatment group, site, subject and visit (where applicable), unless otherwise specified.

Data will be presented in summary tables by treatment group, and visit (where applicable). The category "Missing" will be presented if the number missing is greater than zero for at least one treatment group.

Descriptive summary statistics for continuous variables will include the number of subjects (N), mean, standard deviation (SD), median and range.

Statistical Analysis Plan

Version: Final

Date of Issue: 20 March 2018

Cantex Pharmaceuticals, Inc. Protocol No. CNTX-CX-01 2015 AML I Covance Study ID: 000000146201

Descriptive summary statistics for categorical variables (such as gender, race) will include frequency counts and percentages [n (%)]. Unless stated otherwise in the table shells, the denominator for percentage calculations for a particular variable will be the number of subjects with non-missing data.

Dates will be displayed as DDMMYYYY.

All significance tests will be two-sided and use a 5% significance level except for primary outcome, which is tested at I -sided at 15% level of significance.

7.2 Subject Disposition and Data Sets Analyzed

Subject disposition will be listed and summarized by treatment group and overall and will include the number and percentage of subjects:

- screened;
- randomized;
- randomized and not treated;
- treated;
- available at each study visit (treatment period, 30 day safety follow-up, long term follow-up at every 3 months until approximately 18 months or deaths of all patients, whichever is earlier);
- included in each study population (ITT, PP, Safety).

In addition, the number and percentage of subjects who complete the study and who discontinued early, including a breakdown of the primary reasons as reported in the eCRF for early termination, will be presented for all analysis populations (ITT, PP, Safety). Additional summaries for safety follow up (reasons for not completing safety follow up) and long term follow up (status of long term follow up, cause of death recorded at long term follow up) will be provided for each treatment arm for the ITT, PP and safety population.

A summary of patient enrollment by site will also be provided by treatment group and overall for the ITT population.

A summary of the reasons for screen failure as well as the number of subjects screened but not randomized will be produced. No other information for screen failures will be presented.

7.3 Protocol Deviations

All protocol deviations will be listed and summarized by treatment group for the ITT population.

All important protocol deviations leading to exclusion from the PP population (see Section 5) will be listed and summarized by treatment group for the ITT population.

Statistical Analysis Plan

Version: Final

Date of Issue: 20 March 2018

Cantex Pharmaceuticals, Inc. Protocol No. CNTX-CX-01 2015 J\ML I Covance Study ID: 000000146201

7.4 Demographics and Other Baseline Characteristics

Demographic and baseline characteristics will be listed and summarized by treatment group and overall for all analysis populations (ITT, PP, Safety). Standard descriptive statistics will be presented for the continuous variables of:

- Age at screening (years) [calculated as (informed consent date - date of birth)/365.25 and reported as whole years];
- weight (kg);
- height (cm);
- BMI
- Time since diagnosis
- Baseline blasts in bone marrow(%)
- Baseline LDH

The total counts and percentages of subjects will be presented for the categorical variables of:

- age group (years) (grouped as <70 and 2: 70);
- sex;
- race;
- ethnicity;
- AML type (de novo or secondary);
- Baseline peripheral blasts (Yes/No)
- ECOG performance status
- Time since diagnosis(<= 30 days,> 30 days)

No formal tests of statistical significance will be performed on the demographic and baseline data.

Other baseline measurements, such as bone marrow aspirate/biopsy, pregnancy test result, lab parameters, vital signs, ECG and ECOG, will be summarized by treatment group with the post-baseline measurements.

7.4.1 Medical History

Medical history will be coded using the latest available Medical Dictionary for Regulatory Activities (MedDRA). All medical history will be listed, and the number and percentage of subjects with any medical history will be summarized for some analysis populations (ITT, Safety) by system organ class (SOC) and preferred term (PT) for each treatment group and overall.

7.4.2 Prior, Post treatment (anti AML) and Concomitant Medications

Medications received prior to or concomitantly with treatment will be coded using the WHO Drug Dictionary [March 2016 132 version] Anatomical Therapeutic Chemical (ATC) Classification codes.

Prior, post treatment medications and concomitant medications are defined as follows:

- Concomitant medications are those with a start date on or after the first dose date of study treatment, or those with a start date before the first dose date of study treatment and a stop date on or after the first dose date of study treatment.
- Prior medications will be defined as non-study medication with a stop date prior to the first dose of study treatment.
- Post treatment medications are those with start date after the last dose of study drug.

Concomitant medications will be further divided according to whether they were started before (both prior and concomitant) or after (concomitant-only) the first dose of treatment.

If a medication cannot be classified as "prior" or "concomitant" after applying imputation rules for missing/incomplete dates, it will be classified as concomitant.

Prior anti-AML treatment medications and concomitant medications will be listed and summarized separately for ITT analysis population. Post treatment medications will be listed only.

The number and percentage of subjects using each medication will be displayed together with the number and percentage of subjects using at least one medication within each therapeutic class (ATC-Level 2), chemical subgroup (ATC-Level 4), and generic term.

7.5 Measurements of Treatment Exposure and Study Drug Usage Rate

Extent of study treatment exposure will be summarized for the entire study treatment period and by cycle. Exposure variables will include duration of study treatment, number of dose reductions, number of treatment delays (interruptions), number of treatment cycles, and dose intensity relative to dose levels specified in the protocol.

There are three types of treatment cycles: induction cycle, re-induction and consolidation cycles. For each cycle, the exposure for each drug (Idarubicin, Cytarabine, CX-01) is taken as the sum of duration of drugs for drug taken within that cycle. For drugs that started and ended on the same day, it will be regarded as 1 day, for drugs that started and ended on different days, the duration will be calculated as date of last dose minus date of first dose + 1 day for the period which the drug was administered. Proportion of patients who are exposed to the full expected duration for each component of the study drug will be presented for each cycle.

The study drug usage rate calculation for the induction cycle is as follows, where the expected number of days is the number of days the patients were expected to take the drug, up to the point of study

Statistical Analysis Plan

Version: Final

Date of Issue: 20 March 2018

Cantex Pharmaceuticals, Inc. Protocol No. CNTX-CX-01 2015 AML I Covance Study ID: 000000146201

discontinuation. If a patient was scheduled to take 7 days of drug but only took the drug for 5 days because of early withdrawal, then the expected number of days would be 5.

The calculation of BSA will be based on the best possible results for study drug usage (closest to 100% and below) from Mostellar, Dubois and Gehm, formulae as outlined below.

DuBois[1]

$$BSA (m^2) = 0.007184 \times \text{Height(cm)}^{0.725} \times \text{Weight(kg)}^{0.425}$$

Gehan[2]:

$$BSA (m^2) = 0.0235 \times \text{Height(cm)}^{0.7246} \times \text{Weight(kg)}^{0.51456}$$

Mostellar[3]:

$$BSA (m^2) = ([\text{Height(cm)} \times \text{Weight(kg)}] / 3600)^{0.5}$$

Group 1: Idarubicin + Cytarabine

Idarubicin: Actual total dosage per 1112 / (12 mg/1112 x expected number of days) [Maximum expected number of days=3]

Cytarabine: Actual total dosage per 1112 / (100 mg/1112 x expected number of days) [Maximum expected number of days=7]

Group 2: Idarubicin + Cytarabine + plus lower dose CX-01

Initial CX-01 4 mg/kg, (0 or 100%)

CX-01: Actual total dosage per kg / (3 mg/kg/day x expected number of days) [Maximum expected number of days=7]

Idarubicin: Actual total dosage per 1112 / (12 mg/1112 x expected number of days) [Maximum expected number of days=3]

Cytarabine: Actual total dosage per 1112 / (100 mg/1112 x expected number of days) [Maximum expected number of days=7]

Group 3: Idarubicin + Cytarabine + plus higher dose CX-01

Initial CX-01 4 mg/kg, (0 or 100%)

CX-01: Actual total dosage per kg / (6 mg/kg/day x expected number of days) [Maximum expected number of days=7]

Statistical Analysis Plan

Version: Final

Dale of Issue: 20 March 2018

Canlax Pharmaceuticals, Inc, Protocol No, CNTX-(CX-01 2015 AML I Covance Study ID: 000000146201

Idarubicin: Actual total dosage per 1112/(12 mg/1112 x expected number of days) [Maximum expected number of days=3]
Cytarabine: Actual total dosage per 1112/(100 mg/1112 x expected number of days) [Maximum expected number of days=7]

The study drug usage rate calculation for the re-induction cycle under 5+2 regimen is as follows:

Group 1: Idarubicin + Cytarabine

Idarubicin: Actual total dosage per 1112/(12 mg/1112 x expected number of days) [Maximum expected number of days=2]
Cytarabine: Actual total dosage per 1112/(100 mg/1112 x expected number of days) [Maximum expected number of days=5]

Group 2: Idarubicin + Cytarabine + plus lower dose CX-01

Initial CX-01 4 mg/kg, (0 or 100%)

CX01: Actual total dosage per kg/(3 mg/kg/day x expected number of days) [Maximum expected number of days=5]
Idarubicin: Actual total dosage per 1112/ (12 mg/1112 x expected number of days) [Maximum expected number of days=2]
Cytarabine: Actual total dosage per 1112/ (100 mg/m² x expected number of days) [Maximum expected number of days=5]

Group 3: Idarubicin + Cytarabine + plus higher dose CX-01

Initial CX-01 4 mg/kg, (0 or 100%)

CX01: Actual total dosage per kg/ (6 mg/kg/day x expected number of days) [Maximum expected number of days=5]
Idarubicin: Actual total dosage per 1112/ (12 mg/1112 x expected number of days) [Maximum expected number of days=2]
Cytarabine: Actual total dosage per 1112/ (100 mg/m² x expected number of days) [Maximum expected number of days=5]

The study drug usage rate calculation for the consolidation cycle is as follows:

Statistical Analysis Plan

Version: Final

Date of Issue: 20 March 2018

Cantcx Pharmaceuticals, Inc. Protocol No. CNTX-CX-01 2015 AML I Covance Study ID:000000146201

Group 1: Cytarabine

Cytarabine: Actual total dosage per m²/ (2 g/ m²x expected number of days) [Maximum expected number of days=3]

Group 2: Cytarabine + plus lower dose CX-01

Initial CX-01 4 mg/kg, (0 or 100%)

CXOJ: Actual total dosage per kg/(3 mg/kgx expected number of days) [Maximum expected number of days=5]

Cytarabine: Actual total dosage per 1112/(2 g/ m²x expected number of days) [Maximum expected number of days=3]

Group 3: Cytarabine + plus higher dose CX-01

Initial CX-01 4 mg/kg, (0 or 100%)

CXOI: Actual total dosage per kg/(6 mg/kgx expected number of days) [Maximum expected number of days=5]

Cytarabine: Actual total dosage per 1112/(2 g/ m²x expected number of days) [Maximum expected number of days=3]

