8 CHANGES FROM PLANNED ANALYSES IN PROTOCOL

A new analysis population mITT is added as per client request after the first DSMB meeting.

For primary objective, the time component required (on or after 21 days from date of randomization) for the recognition of morphologic CR is added in the definition.

For secondary objective, the time component required (on or after 21 days from date of randomization) for the recognition of CRi and CRp is added in the definition.

For secondary and exploratory objectives, the following variables are additional to the protocol:

- Duration of composite CR, with the definition of composite CR being clarified as CR or CRi or CRp.
- Days until neutrophil recovery to $2: 500/ \mu\text{L}$
- Days until platelet recovery to $2: 20,000/ \mu\text{L}$

For Leukemia-Free State (LFS), the definition is now changed to from date of leukemia free state, because the protocol definition from date of randomization is not correct.

Repeat of CRi and composite CR in the same fashion as primary efficacy analysis and addition of composite CR for subgroup analysis.

Compliance is termed as study drug usage rate in the SAP.

Competing risk of death analyses will not be performed.

Post treatment medications will only be listed and not summarized as per client request.

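### SAP 7.5 picks the BSA formula by the compliance result it gives, so reported idarubicin and cytarabine usage depends on its own outcome

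*SAP*

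**What the plan says.** SAP 7.5 lists among the exposure variables "dose intensity relative to dose levels specified in the protocol", the same measure that Protocol 6.8.7 plans. It then defines a usage rate for each drug and cycle. The chemotherapy rates are per square metre:

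- "Idarubicin: Actual total dosage per 1112 / (12 mg/1112 x expected number of days"
- "Cytarabine: Actual total dosage per 1112 / (100 mg/1112 x expected number of days"

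The CX-01 rate is per kilogram: "CX-01: Actual total dosage per kg / (3 mg/kg/day x expected number of days" in the lower-dose arm, with the same form in the higher-dose arm. BSA therefore enters only the idarubicin and cytarabine rates.

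On which BSA to use, the SAP says: "The calculation of BSA will be based on the best possible results for study drug usage (closest to 100% and below", chosen "from Mostellar, Dubois and Gehm, formulae as outlined below". It does not say whether the choice is made per patient, per cycle, per drug or once for the study. It also does not say what to do if no formula gives a value at or below 100%.

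SAP section 8 states that "Compliance is termed as study drug usage rate in the SAP", so this is the trial's compliance measure. Section 8 does not list the BSA rule as a change from the protocol. The usage shells (Table 14.1.15 onwards) tabulate the percentage of patients with 100% usage. Listing 16.2.13 shows usage rates but has no column for BSA, formula or dose given.

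**The concern.** A compliance measure should be fixed before the answer is known. Here the denominator is whichever one makes the answer look best without passing 100%. That works in two directions. When both formulas give less than 100%, the rule keeps the higher value, so under-dosing looks smaller. When the formulas fall on either side of 100%, it discards the higher value, so a dose above target by the site's own formula can be shown as a shortfall.

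This is an open-label trial in which CX-01 is added to a chemotherapy backbone, so whether that backbone was delivered equally in the three arms is a fair question. A table of patients at 100% usage is sensitive to shifts of a few points, and a reader of the listing could not undo the selection.

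**Working it through.** The documents give no usage figure to reproduce. Heights, weights and dose variation below are assumptions.

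**Formulas (SAP 7.5).** H is in cm and W in kg.

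- DuBois: "BSA (m^2) = 0.007184" × H^0.725 × W^0.425
- Mosteller: (H × W / 3600)^0.5
- Usage = (total dose / BSA) / (protocol dose per m² × expected days)

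For a given dose, usage by DuBois divided by usage by Mosteller equals Mosteller BSA divided by DuBois BSA. The BSA gap is therefore the room the rule has to move.

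**Size of the gap**

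| Height / weight | DuBois m² | Mosteller m² | Mosteller above DuBois |
|---|---|---|---|
| 155 cm / 50 kg | 1.467 | 1.467 | 0.0% |
| 170 cm / 70 kg | 1.810 | 1.818 | 0.5% |
| 175 cm / 85 kg | 2.007 | 2.033 | 1.3% |
| 165 cm / 100 kg | 2.061 | 2.141 | 3.9% |
| 165 cm / 110 kg | 2.146 | 2.245 | 4.6% |
| 160 cm / 110 kg | 2.099 | 2.211 | 5.4% |

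**Worked case: 165 cm, 110 kg, induction idarubicin.** The target is 12 mg/m² × 3 days = 36 mg/m². That is 36 × 2.146 = 77.3 mg by DuBois and 36 × 2.245 = 80.8 mg by Mosteller.

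- *Under-dosing shrunk.* A dose at 95.0% by Mosteller is 95.0 × 2.245 / 2.146 = 99.4% by DuBois. The rule reports 99.4%.
- *Over-dosing turned into a shortfall.* A dose at 102% by DuBois is 78.8 mg, and 78.8 / 80.8 = 97.5% by Mosteller. The rule reports 97.5%. A dose only slightly high, 100.5% by DuBois, is reported as 96.1%.
- *No answer.* A dose at 105% by DuBois is 100.4% by Mosteller. Neither qualifies, and the SAP names no fallback.

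**Effect on a population (assumed).** Height has mean 170 cm and SD 10; BMI has mean 28 and SD 5. Delivered dose has SD 4% around full dose by the site's formula. The rule is applied per patient with DuBois and Mosteller. The 97% cut-off is illustrative and is not in the documents.

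| Formula the sites dosed by | Under 97% by that formula | Under 97% under the SAP rule | No qualifying formula |
|---|---|---|---|
| Mosteller | 22.6% | 14.3% | about 49% |
| DuBois | 22.6% | 22.4% | about 35% |

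The formulas fall on either side of 100% in about 16% of patients in both scenarios.

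**Check on the obvious remedy.** If sites dosed by DuBois and the SAP imposed Mosteller on everyone, 35.6% would be labelled under 97% instead of 22.6%. A single imposed formula is not neutral.

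**The case against.** The strongest defence is that the rule tries to recover the formula each site used. The protocol names no BSA formula, and Protocol 6.4.2.1 leaves chemotherapy preparation to institutional procedures, so sites may well have differed. Where a patient was dosed at exactly 100% by either formula, the rule does return 100%. But the SAP does not state this aim, and the condition that the value must not exceed 100% defeats it as soon as a dose is slightly high: the 100.5% case above becomes 96.1%. What stands is the warning that imposing one formula on every site would create errors of its own.

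The second defence is that little depends on this measure, and that stands too. The rule is the same in all arms. The Fisher test of CR in SAP 7.6.1 does not use the usage rate, and SAP section 5 defines the per-protocol set by deviations, not by usage. SAP 7.5 and the Table 14.1.31 shell also give exposure measures that need no BSA, such as full expected duration and dose interruptions. Protocol 6.4.4.2 allows no idarubicin or cytarabine modification during induction, the phase that settles the primary endpoint.

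A reader might infer that the usage tables could never reveal a difference in chemotherapy between arms. The documents do not support that. A patient who missed one of three idarubicin days scores 66.7% by the site's formula and, even at a 4.6% gap, at most 66.7 × 2.245 / 2.146 = 69.8%. Gross under-delivery stays visible; differences of a few points are what the rule can blunt or distort.

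**Conclusion.** The concern holds in limited form. SAP 7.5 states a rule under which the BSA formula is chosen by the compliance result it yields, and the rule is incomplete when every candidate exceeds 100%. Its effect on reported idarubicin and cytarabine usage is about 0 to 5 points between DuBois and Mosteller, largest in heavy patients. It is confined to descriptive exposure and compliance tables, including the 100% usage tables. It should be corrected, but it does not threaten the primary result.

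Three limits apply:

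- *Per-patient selection is an inference.* It is the natural reading, because usage is calculated and listed by patient and cycle, but the SAP does not say so. The choice depends on the outcome under any reading.
- *The 22.6% to 14.3% drop in under-dosed patients is not a general estimate.* It assumes dosing by Mosteller. Under DuBois dosing the share barely moves, and the documents do not say which formula sites used.
- *The Gehan formula is not counted as a defect.* Its height exponent reads 0.7246, which gives 8.64 m² at 170 cm and 70 kg. A reader might infer that the SAP would report usage near 20% for some patients. The surrounding text is visibly damaged, so this may be a reading error. The figures above leave Gehan out; a usable third formula could change the range and could only lower the share with no qualifying value.

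**What to change.** In SAP 7.5, delete the best-result rule and replace it with a fixed order:

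1. Compute idarubicin and cytarabine usage with the BSA, or the formula, that the site used for dosing, where this was recorded.
2. Otherwise use one prespecified formula for all patients and all cycles.
3. Report values above 100% as they are.

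Record the change in SAP section 8, and add BSA and its source to Listing 16.2.13 so that a reader can check the rates. Check the Gehan exponent against the original SAP.

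The cost is a few sentences and simpler programming. No new data are needed unless the site BSA is wanted and was not recorded. There are two downsides: reported usage will look slightly less favourable, and where the single fallback formula is applied to a site that used another, usage can be misstated by up to about 5 points. That is why the site's own BSA should come first.

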7.6 Efficacy

7.6.1 Primary Efficacy Analysis

Fisher exact test will be used to compare the proportion of CRs between each dose and control for the ITT population using one sided test at 15% level of significance along with a 70% CI. These tests will be conducted in a fixed sequence: higher dose versus control first and lower dose versus control second, with the second test considered exploratory (failed) if the first test fails.

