Statistical Methods:	
Sample Size A total of 25 evaluable patients per arm will provide 71.8% power for each test comparing a dose with control via a Fisher's exact test at 1-sided alpha = 0.15 to detect a difference between a control proportion 0.55 and an experimental dose proportion 0.80; these tests will be conducted in a fixed sequence: higher dose versus control first and lower dose versus control second, with the second test considered exploratory (failed) if the first test fails.
 
Analysis populations The following populations will be considered for data summaries. Intent-To-Treat (ITT): All randomized patients. Patients will be analyzed according to the treatment to which they are randomized. The ITT Population will be the primary analysis set for the efficacy variables.
 
Per Protocol (PP): Supporting analyses will be conducted on the PP Population, comprising all patients randomized and treated without major protocol violations during the trial. This population will be documented before final database lock.
 
Safety: All patients who received at least one dose of study treatment. Patients will be included in the analyses according to the treatment they received. The Safety Population will be used in the analyses of all safety endpoints.
 
Primary analysis The primary efficacy analyses will be based on the ITT Population. Fisher exact test will be used to compare the proportion of CRs between each dose and control.
 
Secondary analysis The primary analysis will be repeated using the PP Population as a supportive analysis. Complete response rates and confidence intervals will also be reported for key subgroups (e.g., randomization strata). Analyses of EFS, LFS, time to neutrophil recovery, time to platelet recovery, and OS will be descriptive. Kaplan-Meier (KM) estimates will be used to estimate the survival distribution for each arm and KM plots will be produced to accompany these analyses. Confidence intervals will be reported for medians and KM estimates. Duration of response will be analyzed using a similar approach; the analysis will account for the competing risk of death and the survival distributions will be estimated as cumulative incidence functions.
 
Mortality rate at Day 30, Day 60, and Day 90 will be reported using descriptive statistics in a manner similar to the reporting of the morphologic CR rate. The time to neutrophil and platelet recoveries will be reported using the following descriptive statistics: N, mean, standard deviation, median, minimum, maximum, and 1st and 3rd quartiles.

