6. INVESTIGATION PLAN

6.1 Overall Study Design and Plan Description

This is an exploratory phase II, open-label, randomized, multicenter, parallel group trial to determine whether there is evidence that the addition of either or both different dose levels of CX-01 to standard induction therapy (idarubicin + cytarabine) and consolidation therapy has an additive therapeutic effect in newly diagnosed AML patients when compared to patients receiving standard induction chemotherapy alone.

Approximately 75 patients will be randomized in a 1:1:1 ratio to one of the following treatment groups:

- **Group 1:** Idarubicin + Cytarabine, OR
- **Group 2:** Idarubicin + Cytarabine plus lower dose CX-01 (0.125 mg/kg/hour), OR
- **Group 3:** Idarubicin + Cytarabine plus higher dose CX-01 (0.25 mg/kg/hour)

Eligible patients who meet the inclusion criteria and do not meet any of the exclusion criteria and have provided informed consent will be enrolled in the study. Each patient will participate in the study for approximately 18 months from the time of informed consent through final study contact, or until they withdraw from the study or the study is terminated by the Sponsor.

[figure not shown]
Overall survival data will be collected every 3 months until death or until the end of study by the investigational sites. The end of study will occur approximately 18 months after the last patient is randomized.

A Data and Safety Monitoring Committee (DSMC) will meet periodically to review the safety of the study (see Section 6.6.5). Details describing the DSMC process and procedures will be outlined in a separate DSMC Charter.

Adverse events (AEs) will be collected from time of informed consent and continue until 30 days after the last study treatment is administered. Longer follow-up and collection of AEs may be required for patients that do not have an absolute neutrophil count (ANC) recovery within 42 days (i.e., until the recovery or the reason for no recovery is diagnosed) after the last induction or consolidation cycle.

A flow diagram of the study design is shown in Figure 6—1.

Figure 6—1 Study Design

Abbreviations: AML=acute myeloid leukemia

Note: It is expected that approximately 90 patients will be screened to identify 75 patients for randomization.

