6.8 Statistical Methods

6.8.1 Determination of Sample Size

A total of 25 evaluable patients per arm will provide 71.8% power for each test comparing a dose with control via a Fisher's exact test at 1-sided $\alpha = 0.15$ to detect a difference between a control proportion 0.55 and an experimental dose proportion 0.80; these tests will be conducted in a fixed sequence: higher dose versus control first and lower dose versus control second, with the second test considered exploratory (failed) if the first test fails.

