2.6 Sample Size and Power

A total of 25 evaluable patients per arm will provide 71.8% power for each test comparing a dose with control via a Fisher's exact test at I-sided alpha = 0.15 to detect a difference between a control proportion 0.55 and an experimental dose proportion 0.80; these tests will be conducted in a fixed sequence: higher dose versus control first and lower dose versus control second, with the second test considered exploratory (failed) if the first test fails.

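### The one-sided 15% Fisher test has a true size of about 10% at 25 vs 25; Boschloo's exact test stays within 15% and raises power from 71.7% to 80.5% there, with no added patients

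*SAP*

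**What the plan says.** SAP 7.6.1 specifies: "Fisher exact test will be used to compare the proportion of CRs between each dose and control for the ITT population using one sided" and continues "test at 15% level of significance along with a 70% CI". Protocol 6.8.8.1 names the same test. The comparisons run in a fixed sequence, higher dose first; if that test fails, the lower-dose test counts only as exploratory.

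Protocol 6.8.1 gives the sizing: "A total of 25 evaluable patients per arm will provide 71.8% power for each test comparing a dose with control". The test there is "Fisher's exact test at 1-sided alpha = 0.15 to detect a difference", and SAP 2.6 repeats the planning rates: "a difference between a control proportion 0.55 and an experimental dose proportion 0.80". Protocol 6.1 plans about 75 patients, allocated 1:1:1.

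Neither document gives the attained size of the Fisher test at these arm sizes or mentions an unconditional exact alternative. SAP 7.6.3 plans no sensitivity analysis.

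**The concern.** An exploratory phase II trial that accepts a 15% one-sided error has chosen to tolerate more false positives so as to miss fewer real effects. Fisher's test conditions on the total number of remissions, so with 25 per arm it has few attainable p-values and often stops well short of 15%. The leniency that the sponsor chose is then only partly used.

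The stake is power. It matters for both doses, because a missed first test also removes the lower dose from formal testing.

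**Working it through.** **Inputs.** n = 25 per arm, control CR rate 0.55, dose CR rate 0.80, one-sided α = 0.15, stated power 71.8% (Protocol 6.8.1, SAP 2.6); fixed sequence (SAP 7.6.1).

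**Formulas.** Let c and e be the CR counts on control and dose, and b(x; n, p) the binomial probability.
- Fisher p-value: P(c, e) = Pr(X ≥ e), where X is hypergeometric with 50 patients, c + e remissions and 25 drawn.
- Power of a rejection region R: the sum over (c, e) in R of b(c; 25, 0.55) × b(e; 25, 0.80).
- Size at a common rate p: the same sum with p in both places. Maximum size is taken over p from 0.0005 to 0.9995.
- Boschloo: reject when P(c, e) ≤ k, with k the largest cut-off whose maximum size is at most 0.15.

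**Step 1: the plan's own figure.** Summing over all 26 × 26 tables with P ≤ 0.15 gives power 0.7171, against the stated 71.8%. A two-sided 15% Fisher test would give 59.2% and a pooled normal approximation 81.1%, so the plan's figure is the one-sided exact Fisher calculation and already reflects the test's conservatism.

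**Step 2: Fisher's true size.** It is 0.1002 at 0.55, at most 0.1013 (at 0.50), and between 8.6% and 10.1% for rates from 0.50 to 0.80. About 15 − 10 = 5 points of the accepted error are unused.

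**Step 3: Boschloo at 25 vs 25.** The cut-off is k = 0.1965, with maximum size 0.1473. The next attainable cut-off would give 16.1%, so the search stops there. The test rejects every table that Fisher rejects and 14 more. One of these is 14/25 on control vs 18/25 on dose: Fisher p = 0.189, which fails at 0.15 and passes at k.

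| 25 vs 25 | Fisher | Boschloo |
|---|---|---|
| Maximum size | 10.1% | 14.7% |
| Size at 0.55 | 10.0% | 13.9% |
| Power, 0.55 vs 0.80 | 71.7% | 80.5% |
| Both doses succeed, if both have 0.80 | 58.7% | 70.4% |

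The last row is the sum over c of b(c; 25, 0.55) × q(c)², where q(c) is the chance of rejection given the shared control count c. The gains are 80.5 − 71.7 = 8.8 points per test and 70.4 − 58.7 = 11.7 points on the lower dose under the sequence. Fisher would need 30 per arm, 90 patients in all, to reach 80.6%.

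**Step 4: other tests at 25 vs 25.** The exact unconditional pooled-Z test does as well as Boschloo (power 80.6%, maximum size 14.7%). Mid-p Fisher and the uncorrected pooled z test have similar power but maximum sizes of 16.1% and 17.9%, above the limit.

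**Step 5: sensitivity.**
- Rates (25 vs 25): Boschloo gains 8.5 points at 0.50 vs 0.75, 7.3 at 0.60 vs 0.85 and 10.7 at 0.55 vs 0.75.
- Arm sizes (0.55 vs 0.80, every pair from 23 to 27): the gain runs from 0.9 to 9.9 points. With control first, 25 vs 27 gives +0.9; 24 vs 26 gives +1.3 (74.8% to 76.0%); 24 vs 25 gives +6.0, reaching 77.3%; 26 vs 25 gives +6.5; 23 vs 26 gives +9.9. Boschloo's maximum size stays at or below 15% in every pair.

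**The case against.** The strongest case is that nothing is broken. Protocol and SAP agree on a valid, conventional, prespecified test. The trial was sized for that test, the stated power is right, and no error limit is exceeded. A true size below the nominal level is a familiar property of Fisher's test. All of this stands, and it is why the point is an improvement and not an error.

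The power is also not free. Boschloo rejects more tables, so at a common rate of 0.55 the false-positive rate goes from 10.0% to 13.9%, a relative rise of 3.9 / 10.0 = 39%. With both doses null, falsely declaring both goes from 3.3% to 4.9%. A sponsor might prefer the extra protection. That stands as a cost to state, but the rate remains within the 15% already accepted.

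The gain of about 9 points belongs to exactly 25 vs 25. Enrolment is approximate and discontinued patients are not replaced, so the realised gain could be near 1 point.

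Timing is a real limit. The trial is open-label and the SAP is final. SAP 8 records that the mITT population was added at the client's request after the first DSMB meeting, and Protocol 6.6.5 gives the committee a role in examining efficacy. The documents do not say whether the sponsor had seen by-arm results. A late change that turns 14/25 vs 18/25 from failure to success would invite challenge.

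A reader might also infer that the Fisher test will contradict the interval reported beside it ("along with a 70% CI"). The documents do not support this. SAP 7.6.1 names no method for the interval, and the shell for Table 14.2.1 cites Clopper-Pearson under a 95% label. Any rate of disagreement would belong to an interval, such as Newcombe's, that the plan does not specify.

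**Conclusion.** The point holds as a cheap improvement. At 25 vs 25 the planned test works at about 10%, not 15%. An exact test that never rejects less than Fisher and keeps its maximum size at 14.7% adds 8.8 points of power per comparison at the planning rates, and 11.7 points to lower-dose success if both doses have a CR rate of 0.80. Over the near-planned arm sizes the gain per comparison is about 1 to 10 points.

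These figures assume independent binomial counts and the planning rates. The plan calls the 25 per arm evaluable while the primary analysis is ITT with missing CR data counted as non-response; this bears on both tests alike and does not change the comparison.

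Two stronger readings should not be drawn: that 71.8% is miscalculated, because enumeration reproduces it, and that the trial's error control fails, because Fisher errs on the safe side.

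**What to change.** In SAP 7.6.1 and 2.6, Protocol 6.8.1 and 6.8.8.1, the synopsis and the test footnote in the shell for Table 14.2.1:
- Name Boschloo's exact unconditional test at one-sided 15% for each dose against control, in the same fixed sequence. Compute the critical value from the actual ITT arm sizes, with maximum size at or below 15% over all common CR rates. Report Fisher's p-value as supportive.
- Restate power as about 80% for exactly 25 vs 25, and show the range of gains for arms of 23 to 27.
- State that the true false-positive rate at a common CR rate of 0.55 rises from 10.0% to 13.9%.

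Make the change, and document its date, before anyone involved in the decision sees CR data by arm. If that is no longer possible, keep Fisher as primary, state that its attained level is about 10% at 25 vs 25, and report the unconditional exact p-value as supportive.

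The cost is a wording amendment and a short program, with no added patients or data. The downsides are the higher true false-positive rate and a test that readers know less well.
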